### Model Results Presentation

- Adjusted odds ratios (ORs) with 95% confidence intervals (95% CIs) and P-value for each covariates.

### Subgroup Analyses

- Separate analysis for stable and exacerbating patients will be provided.

### Sensitivity Analyses

- N/A

### Supportive Analyses

- N/A

### Endpoint / Variables

- The change of COPD prescription for maintenance

### Model Specification

Univariate / Multivariate (Multinomial) logistic regression

- Dependent variable:  
Stable patients: No change (Remained), Stepped up, Stepped down/Stopped.  
Exacerbating patients: Stepped up (Yes/No)  
Exacerbating patients: Stepped down/Stopped (Yes/No)

- Independent variables: variables defined in 6.1.5 Covariates

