### 6.7.2. Summary Measure

- **The COPD prescription for each maintenance therapy at baseline:**
  - Descriptive analysis of categorized covariates (see 6.1.5 Covariates and Other Strata) will be summarized.
  - Adjusted odds ratios (ORs) and 95% confidence intervals (95% CIs) of each covariates based on univariate logistic regression (see 6.7.4. Model Specification).
  - The number and percentage of patients in each pattern of maintenance treatment will be summarized by the covariates used in the multivariate logistic regression.
  - Separate analyses will be performed for stable and exacerbating patients
- **The disease burden of the patients**
  - Number and percentage in different mMRC score intervals, CAT score intervals, Baseline GOLD 2019 group, Gold grade, numbers of historic exacerbation according to the usage of different historic treatments.
    - mMRC score intervals are defined as : Grade0, Grade1, Grade2, Grade3, Grade4
    - CAT categories are defined as: ≤10, 11-20, 21-30, 31-40.
    - Baseline GOLD 2019 group is defined as: A, B, C, D.
    - Gold grade is defined as: I, II, III, IV.
  - Mean and standard deviation of mMRC score, CAT score, number of historic exacerbations according to the usage of different historic treatments.
  - The above analyses will also be performed for Tier 2 and 3 hospitals separately.
- **The change of COPD prescription for maintenance**

The number and percentage of participants in each category across the different study time points.

The categories are defined as:

Categories	Definition
Stepped up	Adding another maintenance treatment: The latter visit increased by any one or more of LAMA, LABA, or ICS treatments compared to the previous visit.
Stepped down	Withdraw any of the maintenance medication but kept the maintenance treatment: The latter visit reduced by any one or more of LAMA, LABA, or ICS treatments compared to the previous visit.
Stopped	Stopped all LAMA, LABA and ICS treatments.
Switched	Between LAMA and LABA; Between LAMA/LABA and ICS/LABA.
Remained	The LAMA, LABA and ICS combinations in the prescription in the latter visit are the same as the combinations in the previous visit; No LAMA, LABA and ICS in the prescription in the latter visit and previous visit.

The time points are coupled as:

Population	Time points	Summary Measure

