## (2) LAMA, LAMA/LABA, ICS/LABA step up situation

The number and percentage of patients who stepped up or not stepped up to any treatment at the time points (including 1-week follow-up/discharge follow-up compare to pre baseline, 3 months follow up compare to baseline (stable patients) or pre baseline (exacerbating patients), 3 months follow up compare to 1-week follow-up/discharge follow-up) will be calculated.

The definition of step up to any treatment for patients with LAMA: LAMA at baseline switched to MITT, SITT, LAMA/LABA or ICS/LABA.

The definition of step up to any treatment for patients with LAMA/LABA: LAMA/LABA at baseline switched to MITT or SITT.

The definition of step up to any treatment for patients with ICS/LABA: ICS/LABA at baseline switched to MITT or SITT.

Comparison will be considered in two directions. For each specific treatment (LAMA, LAMA/LABA, ICS/LABA), the overall significant test will be conducted to detect the difference of stepping up to MITT and SITT (and LAMA/LABA, ICS/LABA when the treatment at baseline is LAMA; Chi-square test or Fisher's exact test will be used and Bonferroni-corrected P value will be calculated when the P value of Chi-square test or Fisher's exact test is less than 0.05). Additionally, when the stepping up situations is MITT, significant test will be conducted to detect the difference of different baseline treatments. Chi-square test or Fisher's exact test will be used and Bonferroni-corrected P value will be calculated when the P value of Chi-square test or Fisher's exact test is less than 0.05; similarly, for SITT. Chi-square test or Fisher's exact test will be used.

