## (3) MITT, SITT step down situation

The number and percentage of patients who stepped down or not stepped down to any treatment, stopped all treatment or not stopped all treatment at the time points (including 1-week follow-up/discharge follow-up compare to pre baseline, 3 months follow up compare to baseline (stable patients) or pre baseline (exacerbating patients), 3 months follow up compare to 1-week follow-up/discharge follow-up) will be calculated.

The definition of step up to any treatment for patients with MITT: MITT at baseline/pre baseline/1-week follow-up/discharge follow-up switched to LAMA, LABA, LAMA/LABA or ICS/LABA.

The definition of step up to any treatment for patients with SITT: SITT at baseline/pre baseline/1-week follow-up/discharge follow-up switched to LAMA, LABA, LAMA/LABA or ICS/LABA.

Comparison will be considered in two directions. For each specific treatment (MITT and SITT), the difference of stepping down to LAMA, LABA, LAMA/LABA and ICS/LABA will be compared. Chi-square test or Fisher's exact test will be used and Bonferroni-corrected P value will be calculated when the P value of Chi-square test or Fisher's exact test is less than 0.05.

Additionally, when the stepping down situations is LAMA, significant test will be conducted to detect the difference of different baseline treatments; similarly, for LABA, LAMA/LABA, ICS/LABA. Chi-square test or Fisher's exact test will be used.

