#### (4) COPD prescription for maintenance therapy step up situation of different patients

The number and percentage of patients who stepped up or not stepped up to any treatment, stepped down or not stepped down to any treatment at the time points (including 1-week follow-up/discharge follow-up compare to pre baseline, 3 months follow up compare to baseline (stable patients) or pre baseline (exacerbating patients), 3 months follow up compare to 1-week follow-up/discharge follow-up) will be calculated and compared by the following covariates: Age (below 65 years old, 65 years old and above), Gender (female, male), Smoking status (Used to smoke, Current smoking, Never smoking), Cardiovascular Disease (yes, no), Concurrent asthma with COPD (yes, no), Past history of tuberculosis (yes, no), Annual income (KRMB) (<30, 30-80, >80), Gold grade (I, II, III, IV), Baseline CAT score ( $\leq$ 10, 11-20, 21-30, 31-40), Type of hospital (Tier 2, Tier 3), History of exacerbation (None, Moderate, Previous hospitalized).

Chi-square test or Fisher's exact test will be used and Bonferroni-corrected P value will be calculated when the P value of Chi-square test or Fisher's exact test is less than 0.05.

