#### 6.7.3. Population of Interest

The secondary analyses will be based on the enrolled population.

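### SAP 6.7.2 and 6.7.4: Switched is a change category with no level in the stable-patient model, add-and-drop changes meet two definitions at once, and no planned analysis separates ability to step up from the decision when severity is the factor

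*SAP*

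**What the plan says.** SAP 6.7.2 defines Stepped up, Stepped down, Stopped, Switched and Remained, and SAP section 9 repeats the table.

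- Stepped up: "The latter visit increased by any one or more of LAMA, LABA, or ICS treatments compared to the previous visit".
- Stepped down: "The latter visit reduced by any one or more of LAMA, LABA, or ICS treatments compared to the previous visit", with some maintenance treatment kept.
- Switched: "Between LAMA and LABA; Between LAMA/LABA and ICS/LABA".
- Remained: the same combination at both visits, including patients with none of the three classes at either visit.

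SAP 6.7.4 models the change. For stable patients the multinomial outcome is "Stable patients: No change (Remained), Stepped up, Stepped down/Stopped". For exacerbating patients there are two Yes/No outcomes, one for step up and one for step-down or stop. The covariates are those of 6.1.5. Age, Gold grade, CAT score, hospital type and exacerbation history are always included.

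Three additional analyses in 6.7.2 use the same terms:

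- Analysis (2) counts as step up "LAMA at baseline switched to MITT, SITT, LAMA/LABA or ICS/LABA".
- Analysis (3), headed as step down, opens its definition with "The definition of step up to any treatment for patients with MITT".
- Analysis (4) compares by covariate the patients who "stepped up or not stepped up to any treatment, stepped down or not stepped down to any treatment".

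On the population, SAP 6.7.3 says: "The secondary analyses will be based on the enrolled population".

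**The concern.** A multinomial outcome needs levels that do not overlap and that cover every patient. As written, a switcher fits no level if the categories are exclusive. If the definitions are taken literally, the same switcher fits both the step-up level and the step-down level. Two programmers following the SAP could drop these patients, merge them with Remained, or code them as both events. Each choice gives different proportions for a secondary objective and different odds ratios.

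The second issue is interpretation. The Rationale in the protocol wants insight into what physicians weigh when they choose treatment, and SAP section 4 expects triple therapy to be more common in GOLD C&D than in A&B. A patient on all three classes is a non-event for step up whatever the physician thinks. A low step-up odds ratio in more severe patients can therefore arise partly because they have nothing left to add.

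**Working it through.** **The plan's own figure.** SAP section 4 states power above 98% for GOLD group and baseline triple therapy with 375 patients, rates of 24% and 46%, and 66% in A&B. Group sizes are 0.66 × 375 = 247.5 and 0.34 × 375 = 127.5. The pooled rate is 0.66 × 0.24 + 0.34 × 0.46 = 0.3148. The standard errors are √[0.3148 × 0.6852 × (1/247.5 + 1/127.5)] = 0.0506 under the null and √(0.24 × 0.76/247.5 + 0.46 × 0.54/127.5) = 0.0518 under the alternative. Then z = (0.22 − 1.96 × 0.0506)/0.0518 = 2.33, so power is 99.0%. The stated figure holds. No power is given for the change models.

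**Classification.** Take six patterns: none, LAMA, LABA, LAMA/LABA, ICS/LABA and triple (MITT and SITT have the same components). They give 6 × 5 = 30 ordered changes. Applying the 6.7.2 definitions literally:

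| Result | Number | Changes |
|---|---|---|
| Step up only | 12 | none to any (5); LAMA to LAMA/LABA or triple (2); LABA to LAMA/LABA, ICS/LABA or triple (3); either dual to triple (2) |
| Step down only | 7 | LAMA/LABA to LAMA or LABA (2); ICS/LABA to LABA (1); triple to any lower pattern (4) |
| Stopped | 5 | any treated pattern to none |
| Both up and down, also Switched | 4 | LAMA↔LABA; LAMA/LABA↔ICS/LABA |
| Both up and down, not Switched | 2 | LAMA to ICS/LABA; ICS/LABA to LAMA |

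Analysis (2) calls LAMA to ICS/LABA a step up, for that analysis only. ICS/LABA to LAMA is placed nowhere: analysis (2) covers only the reverse move, and analysis (3) only moves down from MITT or SITT. These are types of change. The documents give no patient counts for them.

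**Ability versus decision, step up.** Let t be triple use at the reference visit and p the step-up rate among patients able to step up, equal in both severity groups. The all-patient rate is (1 − t) × p. The t values of 24%/46% are the plan's at-diagnosis rates, borrowed; 10%/20% and all values of p are assumptions.

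| t (A&B / C&D) | p | All-patient rates | OR, C&D vs A&B |
|---|---|---|---|
| 24% / 46% | 10% | 7.6% / 5.4% | 0.69 |
| 24% / 46% | 50% | 38% / 27% | 0.60 |
| 10% / 20% | 10% | 9% / 8% | 0.88 |
| 10% / 20% | 50% | 45% / 40% | 0.81 |

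For example, (0.054/0.946)/(0.076/0.924) = 0.69. If the odds ratio among those able were 1.5, with p of 10–50% in A&B, the all-patient value would be 1.02–0.78 at 24%/46% and 1.31–1.13 at 10%/20%.

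**Multinomial form, stable patients.** Let d be the step-down/stop rate among treated patients and u the untreated share. Then up = (1 − t)p, down/stop = (1 − u)d, Remained = the rest; switching is ignored. With p = d = 20%, t = 24%/46% and u = 10%/10%, A&B gives 0.152, 0.180, 0.668 and C&D gives 0.108, 0.180, 0.712. Step up versus Remained is (0.108/0.712)/(0.152/0.668) = 0.67. Over p of 10–50%, d of 10–40% and several u settings, the ratio is 0.45–0.76 for t of 24%/46% and 0.60–0.97 for 10%/20%.

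**Step-down/stop.** The ratio to Remained is 0.67–0.99 with equal untreated shares (0–20%), 1.04–1.32 with 30%/15%, and 0.56–0.87 with 10%/20%. The documents give no untreated shares, so the direction is undetermined.

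**The case against.** The strongest reply has four parts.

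- **The all-enrolled population is a deliberate choice.** SAP 6.7.3 names it, the objective asks for proportions of patients, and 6.7.2 expressly counts patients untreated at both visits as Remained. This stands. A reader might infer that the all-patient severity odds ratios are biased or invalid. The documents do not support that, because those ratios answer a legitimate question about change among all patients.
- **Analyses (2) and (3) already use regimen-specific denominators.** This also stands in part. Analysis (2) starts from LAMA, LAMA/LABA or ICS/LABA, and analysis (3) from MITT or SITT. Neither is crossed with severity. Analysis (4) looks at severity but does not restrict the denominator.
- **Named Switched pairs naturally override the general wording.** That is a sensible reading, and with analysis (2) it settles five of the six mixed changes. But the SAP does not state it, and it still leaves the stable-patient model with no level for switchers. The dataset specification cited in SAP 11.2 is not in the published text and may hold a rule, so a reader should not infer that switchers will certainly be miscoded.
- **The illustration is not the planned model.** Correct. It is an unadjusted two-group contrast, whereas the GOLD group covariate has four levels and is not a fixed variable. SAP 6.1.5 also allows unnamed further covariates, so starting regimen is not ruled out; it is simply not planned.

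**Conclusion.** The outcome definition is faulty as written. Switched has no level in the stable-patient model and no stated code in the exacerbation models, and six of 30 change types meet two definitions. This follows from the text alone. One change, ICS/LABA to LAMA, stays unresolved even on the most favourable reading. The step-up labels in analysis (3) are a slip.

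The interpretive point is narrower: no planned analysis relates severity to step up among patients who could step up. For step up, the direction of the effect on the all-patient odds ratio follows if triple use at the reference visit rises with severity, as SAP section 4 expects. Its size (0.69–0.60 or 0.88–0.81 under equal rates among those able) rests on assumed change rates, on assumed or borrowed prior use, and on no adjustment. No direction can be claimed for step-down/stop.

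This should be fixed before analysis. It does not touch the primary analysis or the sample size.

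**What to change.** 1. **State one exclusive order for 6.7.2 and 6.7.4.** Stopped; Remained; Switched for the listed pairs; then up or down by net number of LAMA, LABA and ICS components, with any other equal-number swap put in Switched. This places all 30 changes once: 13 up, 8 down, 5 stopped, 4 switched. Other orders would also serve; what matters is that one is written. Correct the step-up labels in analysis (3).
2. **Place switchers in every model.** Give Switched its own level in the stable-patient model, or state in advance how switchers are handled if they are few. Code them No in both exacerbation models.
3. **Keep the all-enrolled models, labelled as change among all patients, and add supportive at-risk models.** Fit separate binary models for step up among patients not on LAMA+LABA+ICS at the reference visit, and for step-down/stop among patients on at least one class. Adjust each for reference-visit regimen. Do not read the all-patient severity odds ratios as willingness to escalate.

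The cost is SAP wording and a few more models on data already collected, without multiplicity adjustment. Denominators shrink. Of 750 patients, the step-up model keeps at most 750 × (0.66 × 0.76 + 0.34 × 0.54) ≈ 514 at 24%/46% prior triple use, or 750 × (0.66 × 0.90 + 0.34 × 0.80) ≈ 650 at 10%/20%, before loss to follow-up. A Switched level may be sparse.

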### 6.1.5. Covariates and Other Strata

The list of covariates and other strata may be used in descriptive summaries and statistical analyses, some of which may also be used for subgroup analyses. Additional covariates and other strata of clinical interest may also be considered.

Covariates	Details
Age	below 65 years old 65 years old and above
Gender	female male
Smoking history	Never smoking Used to smoke Current smoking
Any comorbidity	

• Cardiovascular Disease (CVD defined as ischemic heart disease, heart failure, atrial fibrillation, hypertension): yes vs no

• Diabetes: yes vs no

• Hyperlipemia: yes vs no

• Anxiety or Depression: yes vs no

• Gastroesophageal reflux disease (GERD): yes vs no

• Obstructive sleep apnea syndrome (OSAS): yes vs no

• Concurrent asthma with COPD: yes vs no

• Past history of tuberculosis: yes vs no

Baseline GOLD 2019 group	A B C D
Annual income (KRMB)	<30, 30-80, >80
Proportion of outpatient medical insurance (for COPD treatment) (%)	<33%, 33-66%, >66%
Place of residence	city vs outside city
Educational level	illiterate primary school junior mid-school high-school university
Gold grade (Classification of severity of airflow limitation in	I=Mild II=Moderate

Covariates	Details
CRF)	III=Severe IV=Very severe
mMRC	Grade 0, Grade 1, Grade 2, Grade 3, Grade 4
Baseline CAT score	$\leq 10, 11-20, 21-30, 31-40$ . And it will be as continuous data in Logistic regression.
Type of hospital	Tier 2, Tier 3
History of exacerbation	None, Moderate exacerbation, Previous hospitalised exacerbation; And two level (none and exacerbation) will be used in Logistic regression.
Severity of exacerbation (only for exacerbation cohort)	Mild, Moderate, Severe

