Stable patients	3 months vs baseline	
-Descriptive analysis of categorized covariates (see 6.1.5 Covariates and Other Strata) will be summarized.
 
-Adjusted odds ratios (ORs) and 95% confidence intervals (95% CIs) of each covariates based on univariate multinomial logistic regression (see 6.7.4. Model Specification).
 
-The number and percentage of patients in the change of COPD prescription for maintenance therapy will be summarized by the covariates used in the multivariate multinomial logistic regression.

Exacerbation patients	3 months vs pre baseline	Descriptive analysis of the change of COPD prescription for maintenance therapy.
	1-week/ discharge follow-up vs pre baseline	
-Descriptive analysis of categorized covariates (see 6.1.5 Covariates and Other Strata) will be summarized.
 
-Adjusted odds ratios (ORs) and 95% confidence intervals (95% CIs) of each covariates based on univariate logistic regression (see 6.7.4. Model Specification).

	3 months vs 1-week/ discharge follow-up	
-The number and percentage of patients in the change of COPD prescription for maintenance therapy will be summarized by the covariates used in the multivariate logistic regression.

The above analyses will also be performed for Tier 2 and 3 hospitals separately.

In addition, the following content will also be summarized:

(1) The change of treatment in individual treatments by each maintenance treatment

The number and percentage of patients who stopped or started a maintenance treatment prescription at the time points (including 1-week follow-up/discharge follow-up compare to baseline, 3 months follow up compare to baseline, 3 months follow up compare to 1-week follow-up/discharge follow-up) will be calculated.

The above analyses will also be performed for Tier 2 and 3 hospitals separately.

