### Model Checking & Diagnostics

- Collinearity diagnostics
- The covariates with P-value less than 0.1 in univariate (multinomial) logistic regression and fixed variables (including Age, Gold grade, Baseline CAT score, Type of hospital and History of exacerbation) will be included in the multivariate (multinomial) logistic regression model.

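### The change-of-prescription models count patients who cannot step up, step down or stop as unchanged and have no starting-regimen term, so covariate odds ratios can mix a ceiling or floor with the prescribing decision; the size here is unknown

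*SAP*

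**What the plan says.** SAP 6.7.2 defines stepping up as a gain of components: "The latter visit increased by any one or more of LAMA, LABA, or ICS treatments compared to the previous visit". Stepping down is the mirror image with some treatment kept, and stopping means losing all three. Remained covers an unchanged combination and also the untreated patient who stays untreated: "No LAMA, LABA and ICS in the prescription in the latter visit and previous visit".

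SAP 6.7.4 then sets the regression outcomes. For stable patients there is one three-level outcome: "Stable patients: No change (Remained), Stepped up, Stepped down/Stopped". For exacerbating patients there are two binary outcomes, "Exacerbating patients: Stepped up (Yes/No") and the matching one for stepped down or stopped. No level is given for Switched.

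SAP 6.7.3 fixes the population: "The secondary analyses will be based on the enrolled population". Candidate covariates come from the list in 6.1.5. Those that pass a univariate screen at P<0.1 enter together with "fixed variables (including Age, Gold grade, Baseline CAT score, Type of hospital and History of exacerbation"). Neither list contains the maintenance regimen at the start of the interval. Section 6.1.5 adds only that "Additional covariates and other strata of clinical interest may also be considered". Sensitivity and supportive analyses for these models are marked not applicable.

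The intervals modelled are 3 months against baseline for stable patients and, for exacerbating patients, 1-week or discharge follow-up against pre-baseline and "3 months vs 1-week/ discharge follow-up".

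**The concern.** By the SAP's own definitions two kinds of patient have a fixed answer before any physician decides. Someone on all three components has nothing to add, and someone on none has nothing to withdraw. The models nevertheless treat them as patients for whom no change was chosen.

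This matters when the starting regimen varies with a covariate. The Rationale in the protocol wants to learn which factors physicians weigh. If more severe patients are more often on triple therapy at the start, fewer of them can step up, and severity can appear to discourage escalation when it does not. Forcing severity terms into the model does not help, because their own odds ratios carry the distortion. The P<0.1 screen uses the same outcome, so it can also affect which covariates are selected.

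In exacerbating patients the two intervals are linked. Anyone who reaches all three components by the 1-week or discharge visit cannot step up in the next interval. A factor that truly drives early escalation is therefore pushed downwards in the later model.

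**Working it through.** **The plan's own figure.** The plan gives no figure for the change models. Its only power statement (SAP 4, Protocol 4) concerns triple therapy at baseline: more than 98% with 375 patients, 24% against 46%, a 66/34 split and two-sided 5%.
- Group sizes: 0.66 × 375 = 247.5 and 0.34 × 375 = 127.5. Pooled rate: 0.66 × 0.24 + 0.34 × 0.46 = 0.3148.
- Null SE = √[0.3148 × 0.6852 × (1/247.5 + 1/127.5)] = 0.0506. Alternative SE = √[0.24 × 0.76/247.5 + 0.46 × 0.54/127.5] = 0.0518.
- z = (0.22 − 1.96 × 0.0506)/0.0518 = 2.33, so power is 99.0%. The figure is reproduced and is not in dispute.

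**Ceiling.** Inputs from the plan: 24%, 46%, 66/34, n = 375 per patient group per tier (750 over both tiers). Assumed: these or smaller shares apply at the start of the interval; 40% of eligible patients step up in both groups; Switched is ignored; no other covariates.
- Step-up rate in all patients = (1 − share on all three) × 0.40.
- At 24/46: 0.76 × 0.40 = 0.304 and 0.54 × 0.40 = 0.216. OR = (0.216/0.784)/(0.304/0.696) = 0.63.

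| Share on all three at start, A&B / C&D | Step-up, all patients | All-patient OR, C&D vs A&B | Chance of P<0.05, n = 375 / 750 |
|---|---|---|---|
| 24% / 46% | 30.4% / 21.6% | 0.63 | 44% / 73% |
| 15% / 30% | 34.0% / 28.0% | 0.75 | 21% / 38% |
| 10% / 20% | 36.0% / 32.0% | 0.84 | 12% / 19% |
| 5% / 10% | 38.0% / 36.0% | 0.92 | 7% / 8% |
| equal (24% / 24%) | 30.4% / 30.4% | 1.00 | 5% / 5% |

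The last column uses the two-proportion formula above. At 24/46, varying the assumed step-up rate from 10% to 60% moves the OR from 0.69 to 0.57.

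For the stable three-level outcome, assume also that 10% of each group step down. At 24/46 the odds of stepping up against Remained are 0.304/0.596 and 0.216/0.684, a ratio of 0.62.

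**Floor.** The documents give no untreated share. Assume 30% of treated patients step down or stop in both groups. Untreated shares of 20%/10% give 0.80 × 0.30 = 0.24 and 0.90 × 0.30 = 0.27, OR 1.17. Shares of 30%/15% give 1.29, 10%/5% give 1.08, and equal shares give 1.00.

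**What restriction does.** Among eligible patients both groups step up at 40%, so the OR is 1.00. That follows from assuming one rate for every eligible patient. Let the rate depend on regimen instead: 60% from none, 40% from one component, 20% from two, at either severity. With starting mixes none/mono/dual of 50/20/30 (less severe) and 20/20/60 (more severe):
- Less severe: 0.50 × 0.60 + 0.20 × 0.40 + 0.30 × 0.20 = 0.44.
- More severe: 0.20 × 0.60 + 0.20 × 0.40 + 0.60 × 0.20 = 0.32.
- At-risk OR = (0.32/0.68)/(0.44/0.56) = 0.60, with no severity effect within any regimen.

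So restriction removes the strict ceiling but not differences in regimen mix below it.

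**Price of restriction.** Eligible patients of 375 = 375 × [0.66 × (1 − a) + 0.34 × (1 − b)], where a and b are the shares on all three: 257, 300, 325 and 350 for the four unequal rows. Step-up events are the same with or without restriction: 103, 120, 130 and 140. SE of log OR = √Σ 1/[n p(1 − p)], all patients against eligible: 0.256/0.288 (+12%), 0.239/0.258 (+8%), 0.232/0.244 (+5%), 0.226/0.232 (+3%).

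**The case against.** **The SAP already conditions on starting regimen.** Section 6.7.2 (2) and (3) tabulate and test step-up and step-down by starting treatment, and 6.1.5 leaves room for further covariates. This stands as help to the reader, but those tables do not alter the regressions and the open clause names no variable. For the comparisons in 6.7.2 (4) the text can be read either way: it states no at-risk rule, but its phrase about stepping up to any treatment is one that (2) defines by starting regimen.

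**The objective is descriptive.** The change objective is to assess proportions, and Protocol 5.2 plans regression only for baseline patterns. It is tempting to infer that the all-patient proportions are wrong. They are not. The problem is confined to the covariate odds ratios, which the SAP does plan to report with intervals and P values.

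**The size is not established.** A reader might take 0.63 as the bias to expect. The documents do not support that. The 24% and 46% come from a cited study of prescribing at diagnosis, for GOLD groups. Neither the starting-regimen mix nor any step-up rate is given for this study. Protocol 1 describes under-prescribing and Tier 2 hospitals without the latest therapies, so small triple shares are plausible, and at 5%/10% the effect is minor. The illustration is also unadjusted, whereas the planned models contain other terms.

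**Restriction is not a complete cure.** This stands, as the 0.60 counter-example shows. Adding starting regimen has its own limit: severity influences the regimen, so the adjusted odds ratio answers a narrower question. Neither model suffices alone.

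**Conclusion.** The point holds for the regression models in SAP 6.7.4. As written they include patients who cannot have the event, count them as unchanged, and carry no term for where they started. A covariate associated with starting regimen will have an odds ratio that mixes opportunity with decision. If starting regimen does not differ by that covariate, there is no distortion.

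The all-patient odds ratio runs from 0.63 to 1.00 for stepping up over the starting shares tried, and from 1.29 to 1.00 for stepping down or stopping. These rest on assumed rates of 40% and 30% and on an unadjusted comparison of two groups. They show that the effect can be material, not how large it will be. The primary analysis and the descriptive change proportions are unaffected. This is a cheap improvement that should be made before the models are run.

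**What to change.** Amend SAP 6.7.4, and 6.7.2 (4) to match:

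1. Fit step-up models only in patients not on all three of LAMA, LABA and ICS at the start of the interval. Fit step-down/stopped models only in patients on at least one.
2. Take the start from the interval table in 6.7.2: the baseline prescription for stable patients; past-month medication (pre-baseline) or the 1-week/discharge prescription for exacerbating patients.
3. For stable patients, replace the three-level multinomial with two binary models, each against Remained, because the eligible sets differ. State where Switched patients go, in both the stable and the exacerbation models.
4. Use the same denominators for the tests in 6.7.2 (4), and report numbers at risk by starting regimen.
5. Beside each restricted model report the same model with starting regimen added (none/mono/dual for step-up; mono/dual/triple for step-down/stopped), and read the two together.
6. Keep the all-patient proportions as the descriptive result.

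Cost: no new data, since past-month medication and the visit prescriptions are already collected. Step-up models would use about 257 to 350 of 375 patients under the assumed unequal shares, with a log-OR interval about 3% to 12% wider and no step-up events lost. Stable patients need one extra model, and each restricted model gains a companion.
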